7.0 Risks

1. Risks of the study procedures include:

- a. Phlebotomy: bleeding, infection, possible syncope.

- b. Nerve conduction testing: Possible risk of electrical injury (burn) from stimulation of nerves. The procedure can be uncomfortable, and many individuals find it painful.

- c. Skin biopsy: bleeding, infection from skin biopsy site. Usually a stitch is not needed for hemostasis. Patients are warned not to immerse sites in water for 5-7 days (no baths or swimming). Theoretically numbness from injury to the digital nerve of the finger biopsied is possible but has not been observed in previous studies and was evaluated in cadaver studies to determine that depth used would not approach digital nerves or vessels.

2. Risks of IVIg treatment include:

- a) Rare, serious: venous and arterial occlusion, anaphylactic reactions, kidney damage (which could be irreversible), chemical meningitis, congestive heart failure.
- b) Common, moderate: headache, nausea, myalgias.
- c) Risk of IV access: bleeding, infection, superficial venous thrombus

3. Risks of premedication with acetaminophen and diphenhydramine:

- a) Sleepiness
- b) dry mouth
- c) dry eyes
- d) difficulty with urination
- e) constipation
- f) allergic reactions

8.0 Reporting of Adverse Events or Unanticipated Problems Involving Risk to Participants or Others

Adverse events will be recorded by either the study coordinator or investigators. The investigator, her collaborator [name], and the study coordinator will monitor adverse events. Adverse events will be discussed at committee meetings so that any unanticipated events are evaluated and necessary protocol changes made. Serious adverse events are not anticipated, given the minimal invasiveness of the testing proposed. Because this is not a clinical trial, a formal data safety monitoring board will not be created, but the mentoring committee will act as ad hoc reviewers to evaluate

Protocol Version #8:

Protocol Date:

10/04/2022

appropriateness of recruitment, and review any adverse events, which occur. We will report significant adverse events to CSL Behring, to monitor for any significant risks. The study procedures have been performed in previous studies by the PI with no adverse events.

A physician (either the primary investigator or a member of the GCRC) will perform all testing. The primary investigator will be paged if an adverse event occurs. All subjects will give the coordinator/PI the name and contact information of their primary physician in order to communicate any important medical information which is discovered as part of the study (for example, newly diagnosed diabetes mellitus) to ensure appropriate follow up care.

Any adverse events, such as wound infection will be reported to the IRB and to CSL Behring, either at time of continuing review, or if adverse events are serious and require hospitalization or emergency room visit, they will be reported within 24 hours of when the PI is notified. All patients are encouraged to report any signs of infection or uncontrolled bleeding to the PI and will be given contact numbers to reach the PI. Any minor, adverse events anticipated will be reported in the continuing review 12 months from initial IRB approval.

9.0 Study Withdrawal/Discontinuation

Patients can withdraw from the study at any time. Patients who choose to withdraw from the study will be referred back to their primary physician to resume care. Patients wishing to stop therapy may be discharged from the study. Patients wishing to initiate therapy outside of the study medications allowed will be discharged from the study. Patients can contact the PI, or the study coordinator to let them know of their intent to withdraw. Patients who withdraw after biopsies are performed will be given the option to destroy their tissue samples.

10.0 Statistical Considerations

As this is a pilot study and has never been performed in this population, a formal power calculation has not been performed. A sample of 10 CIDP patients was deemed appropriate to determine if abnormal dermal myelinated pathology exists which can be evaluated in further studies. It is possible patients may have insufficient pathology. This study will provide data for future studies and will enable power calculations. Morphometric analysis of IENF, myelin thickness, intermodal length, etc will be compared using nonparametric Wilcoxon test of means of CIDP patients and healthy controls collected from previous study (18).

The data collected from Aim 1 will also be used for both Aims 2 and 3. The primary outcome measures for segmental demyelination obtained from biopsy will include the number of fibers with segmental demyelination (out of a random sample of 25 fibers), the average length of demyelinated segments, and the number of fibers with sodium channel spreading over denuded axons. As a secondary outcome, clinical outcomes such as MRC scores from the routine standard of care will be also collected.

For Aim 2, signed rank tests will be used to test whether there would be any improvement after treatment in the primary outcomes measured at 3 months and 6 months separately, compared to those measured at the baseline. Also, the outcome measures obtained from confocal vs. fluorescence alone will be compared to examine whether the measurements are similar using a random-effects model along with application of bioequivalence testing methodology.

For Aim 3, to examine whether the primary outcomes and MRC scores are correlated, their correlations will be compared using Spearman rank correlations at 3 months and 6 months separately.

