Aim 1. We will obtain glabrous skin biopsies in 10 CIDP patients to demonstrate increased percentage of myelinated fibers with segmental demyelination using immune-histochemical labeling of myelin and axonal proteins compared to those of historical healthy control and diabetic subjects. We will demonstrate that this method will be able to discriminate CIDP patients from healthy controls and diabetic neuropathy patients.

Aim 2. We will perform follow up biopsies 3 months and 6 months after treatment to demonstrate whether there is decreased segmental demyelination after treatment.

Aim 3. We will compare measurement of segmental demyelination in vivo to medical research council (MRC) scores for muscle strength for each patient.

The overall goal is to provide preliminary data for a future study to demonstrate using SClg and IVIg is efficacious in preventing in vivo segmental demyelination and that this correlates with improvement in patient outcomes.

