Epifluorescence microscopy (Leica DM4000) will be sufficient for identifying and measuring Pan NaV-immunoreactive nodes of Ranvier, length of sections for density calculations, as well as other cutaneous structures. Internodal length will be measured three dimensionally (Metamorph) in confocal-acquired images (Leica LSM510). Quantitative morphometric parameters of dermal myelinated fibers include Meissner corpuscle density (receptors per mm²), the density of their myelinated afferents (fibers per mm², axon diameter (µm), and further characterization of myelin structure in regards to internodal, nodal and paranodal length (µm) will also be calculated. Based on morphologic analyses, additional measures unique to dermal myelinated fibers may be generated and ROC curves developed to determine sensitivity and specificity. Confocal microscopy will be utilized in 3 patients at each site to confirm nodal measurements, myelinated fiber density, and confirm presence of segmental demyelination. Correlation of confocal measurements with florescence measurements will be evaluated to determine whether florescence is sufficient for accurate measurements. The PI and [name] will be analyzing the samples in a blinded fashion, and will train lab technicians in this technique which [name] and [name] have published.

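### Section 10's only between-group test names neither segmental demyelination nor the diabetic group, so the Aim 1 comparison has no matching test and the 20% cutoff is left unused

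*Protocol*

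**What the plan says.** Protocol Section 2.0, Aim 1, has one outcome, the percentage of myelinated fibers showing segmental demyelination. The CIDP values are to be "compared to those of historical healthy control and diabetic subjects", and the protocol undertakes to show that "this method will be able to discriminate CIDP patients from healthy controls and diabetic neuropathy patients".

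Section 10.0 contains a single between-group analysis: "Morphometric analysis of IENF, myelin thickness, intermodal length, etc will be compared using nonparametric Wilcoxon test of means of CIDP patients and healthy controls", the controls coming from an earlier study. It then lists three primary outcomes: "the number of fibers with segmental demyelination (out of a random sample of 25 fibers"), the average length of the demyelinated segments, and the number of fibers with sodium channel spreading. The tests given to these are within the CIDP group. For Aim 2, "signed rank tests will be used to test whether there would be any improvement after treatment in the primary outcomes", and for Aim 3 they are correlated with MRC scores by Spearman's method.

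Section 6.0 describes what is measured on the biopsies. "Quantitative morphometric parameters of dermal myelinated fibers include Meissner corpuscle density", and the list continues with afferent fiber density, axon diameter and internodal, nodal and paranodal length. The same section sets 20% segmental demyelination as the CIDP cutoff, derived from the healthy and diabetic data, and says that ROC curves may be developed for additional measures.

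**The concern.** A protocol may leave analysis detail to an SAP, and an SAP may exist here. This is a different problem. Section 10 does state a between-group analysis, and that analysis does not match the aim it should serve. It names other variables and fixes the comparator as healthy controls. The open-ended end of its variable list could take in more measurements, but it cannot add a comparator group. An SAP that followed Section 10 faithfully would carry the mismatch forward.

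At stake is what a positive result could be said to show. Diabetic neuropathy is the closer differential by the protocol's own rates. A difference from healthy controls, possibly on a variable other than segmental demyelination, could be reported as support for Aim 1 although the planned analysis had not examined diabetes.

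**Working it through.** **1. Aim 1 against the Section 10 test**

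| Element | Aim 1 (Section 2.0) | Between-group test (Section 10.0) |
|---|---|---|
| Outcome | Percentage of fibers with segmental demyelination | IENF, myelin thickness, internodal length (typed as intermodal), and unspecified others |
| Comparators | Healthy and diabetic | Healthy only |
| Discrimination | From both groups | No analysis; 20% cutoff not mentioned |

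Primary outcomes named in a between-group test: 0 of 3. Comparators covered: 1 of 2.

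**2. Section 10 variables against the Section 6 procedures**

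- IENF: no procedure in the biopsy, staining or analysis text.
- Myelin thickness: no procedure there either.
- Internodal length: measured. "Internodal length will be measured three dimensionally (Metamorph) in confocal-acquired images". Confocal imaging is, however, stated for only three patients at each site.

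So 2 of the 3 named variables have no measurement procedure.

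**3. How much harder is the diabetic comparison? (illustration only)**

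The protocol states no power, so there is no figure of its own to reproduce.

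Inputs from the protocol: 10 CIDP patients (Section 10.0); means of 5% in healthy and 7.7% in type 2 diabetic subjects (background section); SD 4.1 percentage points (Section 6.0).

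Assumptions, because the protocol does not give them: two-sided alpha 0.05; m = 10 to 30 historical controls per group; CIDP mean of 10%, 12% or 15%; the same SD in every group; normal data.

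Formula: SE = 4.1 × √(1/10 + 1/m); power ≈ Φ(difference/SE − 1.96).

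Worked case, m = 20 and CIDP mean 10%: SE = 4.1 × √0.15 = 1.588.
- Against healthy: 5.0/1.588 − 1.96 = 1.19, power 0.88.
- Against diabetic: 2.3/1.588 − 1.96 = −0.51, power 0.30.

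| Assumed CIDP mean | Power vs healthy, m = 10–30 | Power vs diabetic, m = 10–30 |
|---|---|---|
| 10% | 0.78–0.92 | 0.24–0.34 |
| 12% | 0.97–1.00 | 0.65–0.82 |
| 15% | 1.00 | 0.98–1.00 |

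Simulated rank-sum tests (4,000 runs per case) on the same assumptions run a little lower with the same pattern. With 20 to 30 controls they give 0.82–0.88 against 0.25–0.30 at 10%, and 0.98–0.99 against 0.69–0.77 at 12%. At 15% with 10 to 30 controls, the diabetic comparison has 0.94–1.00.

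**4. A significant rank test is not discrimination**

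Under the same normal model, the share of CIDP patients above the 20% cutoff is 1 − Φ((20 − mean)/4.1):
- mean 10%: 1 − Φ(2.44) = 0.7%
- mean 12%: 1 − Φ(1.95) = 2.6%
- mean 15%: 1 − Φ(1.22) = 11%

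At a mean of 15%, both rank tests would almost always be significant, yet the cutoff would identify about one patient in nine. The location comparison and the diagnostic question therefore need separate analyses.

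**The case against.** The best defence has four parts.

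First, a reader might infer that the Section 10 test uses only quantities the study does not collect. That is not supported: internodal length is measured and listed in Section 6.0, and the open-ended list could include other measured parameters. The objection stands, and the point is limited to IENF and myelin thickness.

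Second, a reader might infer that the protocol has no Aim 1 rule involving diabetes. That is not supported either. The 20% cutoff in Section 6.0 was set with healthy and diabetic data in view, including an upper percentile taken across both groups. What remains is that no sensitivity, specificity or success rule is attached to the cutoff and that Section 10 does not use it. The ROC sentence is optional and concerns additional measures.

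Third, a reader might treat the power gap as established harm. It depends on assumed CIDP means of 10–12%, which sit badly with the protocol's expectation that a 20% cutoff will be sensitive enough, and it largely disappears at 15%. The normal model is also rough: with mean 5 and SD 4.1 it gives Φ(−5/4.1) ≈ 11% of healthy controls a negative percentage. Modest elevations remain possible, since Section 10.0 allows that pathology may be insufficient and Section 4.0 admits patients already treated for up to six months. The figures remain an illustration.

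Fourth, this is a hypothesis-generating pilot, and both comparators are already stated in Aim 1. That excuses the missing power calculation and makes the urgency arguable. It does not excuse a stated test that addresses a different question from the aim.

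**Conclusion.** The point holds in this form: Section 10's one between-group test names neither the Aim 1 outcome nor its diabetic comparator, two of its three named variables have no measurement procedure, and the 20% cutoff has no analysis attached. This rests on the text alone and needs no assumption.

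The numerical consequence is conditional. If CIDP values are only modestly raised (assumed mean 10–12%), success against healthy controls says little about success against diabetic subjects. At an assumed mean of 15% or more, both comparisons would very probably succeed. The protocol gives no expected CIDP mean or historical control numbers with which to choose between these cases. As the study is a pilot, this is a mismatch to put right before the biopsies are analysed and not a flaw that undermines the study.

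**What to change.** Replace the between-group sentence in Section 10.0 with text that does the following.

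- **Location comparison.** Compare the baseline percentage of fibers with segmental demyelination by Wilcoxon rank-sum test, (i) CIDP versus historical healthy controls and (ii) CIDP versus historical diabetic subjects, each with an interval estimate for the difference.
- **Discrimination.** Report separately the sensitivity of the 20% cutoff in CIDP and its specificity in the healthy and in the diabetic group, with exact confidence intervals, and the ROC curve if one is used. State that discrimination from diabetes will not be claimed on the healthy-control comparison alone.
- **Supporting comparisons.** Keep the other two primary outcomes (demyelinated segment length, sodium channel spreading) and the morphometric parameters measured under Section 6.0 in this role.
- **Wording.** Delete IENF and myelin thickness, or add their procedures to Section 6.0. Correct the spelling of internodal. Drop the reference to means, since the Wilcoxon test is a rank test.

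An age-adjusted or age-restricted sensitivity analysis against the historical controls is optional.

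Cost: a few sentences and a few more analyses of historical data that Aim 1 already relies on, with no new patients or biopsies. A claim of discrimination becomes slightly harder to make.

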4.0 Inclusion/Exclusion Criteria

Inclusion Criteria:

1. Adults (age \geq 18 years) with definite or probable CIDP according to the EFNS/PNS criteria may enter the trial within 6 months of treatment onset or treatment naïve patients. Written informed consent is obtained by the local investigator before entry into the study.
2. IVIg treatment of 0.8 up to 1.2 g/kg per 30 days will be allowed up to 6 months. It is expected some patients may be on variable treatment regimens, and as long as they are not significantly declining, efforts will be made to continue treatment regimens already instituted.
3. Prednisone in doses up to 20 mg /day will be allowed as long as dose has been stable for 90 days and is not being escalated or tapered during study.

4. Previous plasma exchange will be allowed as long as it is not continued during the study.

Exclusion Criteria:

1. Other causes of polyneuropathy, multifocal motor neuropathy, diabetes mellitus, alcohol, family history of neuropathy, monoclonal gammopathy or malignancy, history of drug or toxin exposure, which could reasonably cause neuropathy. Coexistent monoclonal gammopathy will also be used as an exclusion as these patients may not have the same response to IVIg.
2. Any other disease that may cause neurological symptoms and signs or that may interfere with treatment or outcome assessments.
3. Severe conditions that may interfere with an evaluation of the study product or satisfactory conduct of the study such as current malignancy or history of allogeneic bone marrow/stem cell transplant, cardiac insufficiency (New York Heart Association Classes III/IV), cardiomyopathy, cardiac arrhythmia requiring treatment, unstable or advanced ischemic heart disease, congestive heart failure or severe hypertension, chronic kidney disease deemed too severe to safely use IVIg, known hyperprolinemia, known bleeding disorders, severe skin disease at the planned injection sites or biopsy site, alcohol, drug or medication abuse.
4. History of keloids or other reactions to local anesthetic making skin biopsies unsafe.
5. Patients with the following laboratory results:
 - a. Positive result at screening on any of the following viral markers: human immunodeficiency virus-1 or 2, or hepatitis B or C virus.

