6.0 Study Procedures

Day -30 -0, Visit 1: Screening visit:

Procedures:

Consent: Patients will provide written consent according to the principles of the 2018 Common Rule and Declaration of Helsinki

H&P: Detailed history and physical with neurological examination will be performed.

MRC score: Medical Research Council (MRC) score for muscle strength will be performed.

Nerve Conduction Studies: Limbs will be warmed to at least 31 C minimum temperature. Antidromic sensory nerve conduction studies of the sural, median and ulnar nerve will be performed. Motor conduction studies of the peroneal, tibial, ulnar and median with proximal studies and F-waves will be performed. Unless patients have significant asymmetry, all studies will be done on the left. Conduction block and temporal dispersion will be noted.

Labs: Blood will be drawn for CBCPD, IgA, CMP. If previously performed will record CSF protein and cell count.

If patients are found to have history and exam consistent with CIDP, met ENFS criteria (cite), inclusion, exclusion criteria including less than 6 months of treatment for CIDP

Protocol Version #8:

Protocol Date:

10/04/2022

they will be accepted into the study and baseline visit will be scheduled 24 hours to 30 days apart. No randomization will take place as all patients will be treated.

Day 1, Visit 2: Baseline visit:

Patients qualifying for the study will be invited back for baseline visit. If patients have not been on IVIg treatment this visit will be scheduled as soon as possible to avoid delays in treatment. If patients have been started on IVIg treatment, patients will be scheduled the day before their next infusion to approximate a nadir in treatment for best baseline measurement.

Procedures:

Physical exam: Interval history will be taken (if appropriate) and physical exam with neurological examination repeated.

MRC score: MRC score will be documented.

INCAT score: The INCAT score will be collected as a secondary endpoint as it has been used in both ICE and PATH studies (refs). The INCAT score for upper and lower extremities will be documented.

Skin biopsies:

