Treatment naïve patients will be initiated on IVIg treatment after baseline visit procedures are completed. This can occur later that day or within the next 14 days. Patients who are treatment naïve will be given a loading dose of 2 g/kg IV over 3-5 days at standard infusion rates which will take 4-6 hours daily, depending on comorbidities and age. Patients will receive acetaminophen and diphenhydramine as standard pre-infusion prophylactic treatment. Patients will receive Privigen which is FDA approved for CIDP treatment either at Vanderbilt University Medical Center hospital infusion center or outpatient infusion center depending on insurance. Patients will then have 1 g/kg IVIg infusions scheduled every 3 weeks for 6 months. Every attempt will be made to ensure Privigen will be used for IVIg product as it is FDA approved for CIDP, is temperature stable, and has no sucrose (26). No placebo will be used given this would be unethical. Patients will serve as their own controls, and the hypothesis is that percentage of segmental demyelination found should decrease as INCAT score and strength increases.

For patients previously treated:

Baseline visit will be arranged closest to the day prior to infusion to ensure the best possible baseline measurement. They will resume according to the patient's previous schedule. Patients will have up to 1.2 g/kg monthly to account for different patient management schedules and variation and patients will be on Privigen ideally.

Patients with escalating weakness not responding to IVIg will be allowed to try additional treatments but will be released from study. Additional treatment with prednisone up to 20 mg/day will be allowed but must be stable dosing and not escalating to avoid additional variability.

Patients will receive IVIg infusions q3 weeks. A monthly phone call will occur so the coordinator can confirm that patients are doing well, having no new treatment related side effects, and are receiving IVIg infusions either at home or in infusion centers.

Day 90, Visit 3:

Procedures (previously described):

History & Physical Exam: Note interval history.

MRC Score

INCAT Score

Skin Biopsy

Labs: BMP to check renal function

Day 180, Visit 4:

Procedures (previously described):

History & Physical Exam: Note interval history.

MRC Score

INCAT Score

Skin Biopsy

Labs: BMP to check renal function

Nerve conduction studies will be repeated from Baseline visit 1

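### Aim 3 correlates biopsy and strength across patients at single visits, so it does not address the protocol's within-patient hypothesis; an exploratory change correlation would, using data already scheduled

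*Protocol*

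**What the plan says.** Protocol section 10.0 fixes the Aim 3 method for the primary biopsy outcomes and MRC: "their correlations will be compared using Spearman rank correlations at 3 months and 6 months separately". It names no change from baseline, whereas the Aim 2 text just above it does compare with baseline.

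Section 2.0 words Aim 3 neutrally, as an intention to "compare measurement of segmental demyelination in vivo to medical research council (MRC) scores for muscle strength for each patient". The overall goal in the same section is preliminary data for a future study of whether treatment prevents demyelination and whether "this correlates with improvement in patient outcomes".

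Section 6.0 (IVIg infusions) goes further. It says "Patients will serve as their own controls", and then that "the hypothesis is that percentage of segmental demyelination found should decrease as INCAT score and strength increases".

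The population is mixed. Section 4.0 admits treatment-naive patients and those who "may enter the trial within 6 months of treatment onset". Under section 6.0, treatment-naive "patients will be initiated on IVIg treatment after baseline visit procedures are completed", while already-treated "patients will be scheduled the day before their next infusion to approximate a nadir in treatment".

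Biopsy, MRC and INCAT are all scheduled at baseline, Day 90 and Day 180 (Appendix A).

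**The concern.** The section 6.0 hypothesis is about co-movement within a patient. The planned Aim 3 statistic asks something else: whether, at one visit, patients with more demyelination are weaker than other patients. The planned change analyses (the Aim 2 signed rank tests and the repeated measures in section 6.0) concern the biopsy outcomes alone. INCAT, named in the hypothesis and collected as a secondary endpoint, enters no planned correlation.

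The study is meant to supply preliminary data and to enable power calculations for a later study of improvement. A strong single-visit correlation could be carried forward as evidence that the biomarker tracks improvement when it shows only that severely affected patients are severe on both measures.

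**Working it through.** The protocol gives no power, alpha or expected correlation for Aim 3, so there is no stated figure to reproduce.

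**Inputs from the protocol:** 10 completers; 25 fibres per biopsy; a change above 5% regarded as meaningful; mixed prior treatment.

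**Assumed:** mean demyelination 30% falling to 22%; SD of patients' stable levels 5 to 20 points; SD of true change 5 to 10 points; MRC with the same level-to-change ratio and a per-visit error of 0 or 0.7 change SD; two-sided alpha 0.05 (critical |rho| 0.648 at n = 10).

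**1. Why one visit cannot separate level from change.** Write each follow-up value as level + change, with the two parts independent and the same SD ratio for both measures. The single-visit correlation is then

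r(visit) = (r(L)·SD(L)² + r(C)·SD(C)²) / (SD(L)² + SD(C)²).

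- SDs 1 and 0.5, levels -0.8, changes 0: -0.8 × 1/1.25 = -0.64.
- Same SDs, levels 0, changes -0.8: -0.8 × 0.25/1.25 = -0.16.
- Equal SDs: -0.40 in both cases, so they cannot be told apart.

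Simulated Spearman averages at n = 10 without counting error agree: -0.57, -0.14 and -0.35 (both equal-SD cases).

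**2. Adding the 25-fibre count.** Each setting had 20,000 simulated trials with binomial counts; true proportions were clipped to 0-1. Ranges are over the assumed SDs.

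| Truth | Planned single-visit rho (average) | Raw change rho (average) |
|---|---|---|
| Changes -0.8, levels unrelated | -0.12 to -0.31 | -0.26 to -0.44 (-0.19 to -0.31 with MRC error) |
| Levels -0.8, changes unrelated | -0.23 to -0.54 (-0.20 to -0.51 with MRC error) | about 0 |

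When both correlations are -0.8 and MRC is error-free, p < 0.05 occurs in 29-65% of trials for the planned statistic and 11-26% for change.

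**3. Mixed prior treatment.** Suppose 3, 5 or 7 of 10 patients are naive (drop of 10 or 16 points, MRC gain of 1 or 2 change SDs), the others have no mean change, and there is no patient-level link. The raw change correlation averages -0.08 to -0.39. A partial Spearman correlation (ranks centred within prior-treatment group) is within 0.01 of 0. With 5 naive patients and a within-group correlation of -0.8, raw is -0.28 to -0.58 and adjusted -0.18 to -0.43.

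**4. Precision of the change score.**

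- SE of one patient's change, 20% to 15%: √[(0.20×0.80 + 0.15×0.85)/25] = 10.7 points. For 30% to 22%: √[(0.30×0.70 + 0.22×0.78)/25] = 12.4 points. Both exceed the 5% called meaningful.
- Reliability of change: with change SD 5, 25/(25 + 152.6) = 0.14; with SD 10, 100/(100 + 152.6) = 0.40. A true -0.8 shrinks to -0.8×√0.14 ≈ -0.30 or -0.8×√0.40 ≈ -0.50 even with error-free MRC.
- 95% interval for an adjusted rho of -0.5 at n = 10: Fisher z = -0.549, SE = √[(1 + 0.5²/2)/6] = 0.433, giving about -0.88 to +0.29. Within a group of 5, using n - 3 = 2, SE = 0.75 and the interval is about -0.97 to +0.73 (rough at that size).

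**The case against.** The strongest reply is that nothing here is an error. The analysis meets Aim 3 as worded, Aim 2 covers the main section 2.0 hypothesis, and exploratory change correlations could sit in a SAP that is not shown. The section 6.0 sentence is neither an aim nor an endpoint, and it may mean only that biopsy and strength both improve under treatment. On that reading, adjusting for prior treatment removes part of the very covariation the sentence predicts. The change score is also weak. With MRC error, a true change correlation of -0.8 and unrelated levels, it reaches p < 0.05 in only 8-14% of trials. With both SDs at 5 points, the planned statistic (-0.21) even averages slightly stronger than change (-0.19). Every magnitude is assumed, and MRC was simulated as continuous, without ties or a ceiling.

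Much of this stands: the change correlation is imprecise and attenuated, offers no power gain, and depends on assumed inputs for its size. It does not remove the point. Section 10.0 does fix the Aim 3 method, and that method does not match a hypothesis the protocol states. Even on the weaker reading, no change analysis is specified for MRC or INCAT. Which estimate is wanted, raw or adjusted, is a genuine choice, so both should be shown. The structural result in step 1 does not depend on the assumed percentages.

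**Conclusion.** The point holds as a minor, optional improvement. The planned correlations answer a between-patient question and can be clearly negative with no change relation (averages of -0.23 to -0.54 under the assumed SDs and a level correlation of -0.8). The change correlation averages about 0 in that case, provided prior treatment status is taken into account in this mixed population. With about 10 completers and 25 fibres it can serve only as a preliminary estimate, and it should not be used uncorrected to plan a later study. The sizes rest on assumed means, SDs, treatment mix and MRC error; the mismatch between method and hypothesis does not.

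**What to change.** Keep the planned 3- and 6-month correlations. In section 10.0, add as exploratory estimates with confidence intervals:

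- Spearman correlation of change from baseline in segmental demyelination percentage with change from baseline in MRC, and likewise in INCAT with its scoring direction stated, at 3 and 6 months (2 scores × 2 visits = 4 estimates).
- The same four adjusted for prior treatment status, for example by partial Spearman correlation, with the change relation plotted within each group.
- A statement that the estimates are imprecise and biased toward zero.

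If a repeated-measures within-patient correlation over the three visits is preferred, include visit and visit-by-prior-treatment terms. With no patient-level link and 5 naive and 5 treated patients, visit terms alone left averages of -0.06 to -0.28; adding the interaction brought them to about 0. A baseline correlation is optional description and does not answer the within-patient question.

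The cost is wording only: no new visit, biopsy or score is needed, and prior treatment status is known at entry. Adjustment costs one degree of freedom (critical |rho| at n = 10 moves from 0.648 to 0.666). The downside is a few more exploratory estimates with wide, attenuated intervals.
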